### Determination of Subjects for Analysis

Rates of adverse events for subjects randomized to OFF will be calculated over the full period of follow-up, while rates of adverse events for subjects randomized to ON will be calculated only during the period that subjects were actually receiving elevated night pacing.

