## 5. Introduction

### 5.1. Background

An estimated 8.5 million people in the United States will have heart failure (HF) by 2030 [1], and approximately 50% of these HF patients will have a preserved ejection fraction (HFpEF) [2]. In contrast to HF with reduced EF (HFrEF), no effective drug or device therapies have been identified that improve the prognosis of the disease.

A large proportion of HFpEF patients have hypertension and have a concentric hypertrophic (CH) etiology described as an increased heart mass with increased relative wall thickness [3]. Cardiomyocytes in HFpEF are thicker than HFrEF, and collagen content is increased compared to controls [4]. Patients with concentric hypertrophy or evidence of increased wall thickness are characterized by an increase in end diastolic pressures and isovolumic relaxation time [5] compared to normal controls. HFpEF patients have relatively normal volumes and EF, but they have a reduced ability to adequately fill a stiffened left ventricle (LV). The impact of this diastolic dysfunction is more notable during exercise; HFpEF left ventricles are reliant on high left atrial pressures to fill the LV [4]. A search for a therapy that improves the compliance of the ventricle and improves early diastolic filling in these patients has not been successful.

We are proposing a pacing therapy that titrates a bolus of atrial pacing at 100 bpm delivered during sleeping hours with the hypothesis that raising heart rates can promote a beneficial LV dilation, which will reduce chamber stiffness and improve diastolic filling in HFpEF patients that have thickened ventricular walls and normal to small LV volumes. One challenge is finding a therapeutic heart rate dose that does not cause undesirable symptoms in ambulatory HF patients and a dose that achieves a desirable level of dilation to improve filling. Studies in animal models show that the dilatory effects of rapid pacing diminishes once the elevated pacing rates are discontinued [6-8] ; the study of dose response to elevated atrial pacing rate also includes monitoring the reaction of the heart to withdrawal of the pacing therapy.

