### 10.12.1. Programming Recommendations

Table 8 lists the programming recommendations applicable to study subjects who still have elevated night pacing ON. (All subjects should have elevated night pacing OFF by the end of the 8 week visit.)

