## Determination of Subjects for Analysis

All adverse events reported for subjects actively receiving elevated night pacing will be included.

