### Analysis Methods

The adverse event reporting rate during the period from week 4 to week 8 in subjects in the ON arm and OFF arm will be compared and characterized.

The Mean Cumulative Function will be used to compare the adverse event reporting rate between the ON arm and the OFF arm. This analysis will be in the framework of the Andersen-Gill model, which is a generalization of Cox's proportional hazard model, comparing the distribution of events between groups and accounts for multiple events within a subject. To execute this analysis, a data set will need to be derived from the data set of all adverse events that occurred in randomized subjects ordered by subject, using SAS code similar to

```
PROC SQL NOPRINT;
  CREATE TABLE Adverse_MCF_Setup AS SELECT pt, trt, randomdt,
    exitdate, aestdt
  FROM A_Adverse
  WHERE ^MISSING(randomdt)
  ORDER BY pt, aestdt;
QUIT;
```

The variables TStart and TStop will be coded as 0 or 1, with the initial value of TStart for each subject equal to the 0, representing the randomization date. TStop will be the number of days until either an event or censor. Each subsequent TStart will be the previous TStop value in days and the corresponding TStop date will be the sum of the value of TStart and the number of days until the next event or censor. That data set will be constructed using SAS code similar to

```
DATA Adverse_MCF;
  SET Adverse_MCF_Setup;
  BY pt aestdt;
  RETAIN prev_stop;
  IF first.pt THEN DO;
    Tstart=0;
  /*  No adverse events - first record*/
  IF MISSING(aestdt) THEN DO;
    Tstop=exitdate-randomdt;
    status=0;
  END;
  ELSE DO;
    Tstop=aestdt-randomdt;
    status=1;
    prev_stop=Tstop;
  END;
  OUTPUT;
END;
ELSE IF ^MISSING(aestdt) THEN DO;
  Tstart=prev_stop;
  Tstop=aestdt-randomdt;
  status=1;
  prev_stop=Tstop;
  OUTPUT;
  IF last.pt THEN DO;
    Tstart=aestdt-randomdt;
    Tstop=exitdate-randomdt;
    status=0;
    OUTPUT;
  END;
END;
RUN;
```

A data set with a single variable trt with two rows with values 0 and 1 (representing the control and treatment arm) will be created and the analysis will then be implemented using SAS code similar to

```
PROC PHREG DATA=Adverse_MCF COVS(aggregate) covm PLOTS(overlay)=MCF;
  MODEL (Tstart, Tstop)*status(0)=trt;
  BASELINE covariates=IN2 out=OUT2 cmf=_all_ / NOMEAN;
```

```
ID pt;  
RUN;
```

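### The randomised week 4 to 8 adverse-event comparison has three incompatible time windows, and one of them applies an on-treatment rule to the ON arm only

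*SAP*

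**What the plan says.** SAP 7.9.3 (Adverse Events – 8 weeks) defines the observation window in three places.

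- **Stated period.** The Analysis Methods name what is to be compared: "The adverse event reporting rate during the period from week 4 to week 8 in subjects in the ON arm and OFF arm". That is one window for both arms.
- **Sample code.** The text says that "a data set will need to be derived from the data set of all adverse events that occurred in randomized subjects". Time starts at randomisation and follow-up closes with "Tstop=exitdate-randomdt", so both arms run to study exit. The extract carries randomisation, exit and event dates, but no pacing-stop date and no 8 week visit date.
- **Subject rule.** "Rates of adverse events for subjects randomized to OFF will be calculated over the full period of follow-up", whereas "rates of adverse events for subjects randomized to ON will be calculated only during the period that subjects were actually receiving elevated night pacing".

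Protocol 14.1.3 contains the stated period and the same subject rule. SAP 7.10, which lists known errors in the protocol's statistical section, does not mention the conflict.

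Three other provisions bear on it. The 4 week AE analysis is limited to time on therapy: "All adverse events reported for subjects actively receiving elevated night pacing will be included". Protocol 10.12.1 ends pacing in the ON arm: "All subjects should have elevated night pacing OFF by the end of the 8 week visit". AEs are collected from consent throughout the study (Protocol Synopsis, Safety Assessments; 12.1).

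**The concern.** A programmer cannot satisfy all three definitions, and the choice affects which events are counted. SAP 7.2 and 7.8 allow analysis while the study is running, so the choice could be made with data in view.

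The subject rule is the most troublesome of the three. It keeps OFF subjects under observation whatever happens to them and drops ON subjects once pacing stops. Stopping is not random:

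- Protocol 10.19 allows pacing to be programmed off for symptoms that reprogramming does not resolve.
- Protocol 10.11 covers a subject randomised to ON whose 4 week NT-proBNP, troponin or LVEF is abnormal. If the investigator elects to discontinue, pacing is turned off at a later visit and the subject is still followed to week 12.

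The second case shows the problem most clearly. An ON subject with an abnormal marker may contribute only a few days, and an OFF subject with the same marker contributes everything. The arms are then no longer comparable.

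Protocol Section 14 treats the ON versus OFF contrast as indicative of longer-term safety, and safety is part of the primary feasibility objective (10.19).

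**Working it through.** The documents give no expected AE rate, effect size or power for this comparison, so there is no figure of theirs to reproduce.

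**1. Window lengths.** From Protocol Table 5, in days after Baseline: randomisation 21–35, 8 week visit 49–63, exit 77–91.

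- ON while paced: nominally 56 − 28 = 28 days; range 49 − 35 = 14 to 63 − 21 = 42.
- OFF, if full follow-up means to exit: nominally 84 − 28 = 56 days; range 77 − 35 = 42 to 91 − 21 = 70.
- ON time left out after week 8: 84 − 56 = 28 days per subject, half of the 56 post-randomisation days. If all 30 paced subjects are randomised 2:1 (20 ON, 10 OFF; an assumption), that is 20 × 28 = 560 person-days.

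**2. Hand example of early stopping (assumed counts).** Take 20 ON subjects over 28 days. Three stop on day 7, and 5 events occur in paced time.

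- Rate under the subject rule: paced time is 560 − 3 × 21 = 497 days, so 5/497 × 28 = 0.28 per 28 days.
- As randomised, if each stopper has one later event: 8/560 × 28 = 0.40. The rule understates ON by 30%.
- As randomised, if no stopper has a later event: 5/560 × 28 = 0.25. The rule overstates ON by 13% (0.28/0.25).

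The 30% figure implies a post-stop rate of 3/63 × 28 = 1.33 per 28 days, 4.7 times the paced rate. The example shows the mechanism and that the sign can change. It is not an estimate.

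**3. Simulated Andersen-Gill hazard ratios (ON/OFF).** There were 40,000 subjects per arm. Assumptions: OFF rate 0.5 AE per 28 days; follow-up continues after pacing stops; OFF runs to day 56 under the written rule. The common window is week 4 to 8 as randomised. With about 20,000 OFF events by week 8 and at least as many in ON, the standard error of the log hazard ratio is about √(2/20,000) = 0.01.

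| Assumed scenario | Written rule | Common window | ON week 4–8 events dropped |
|---|---|---|---|
| Equal constant rates, no early stopping | 1.02 | 1.02 | 0% |
| ON ×1.5; 30% of paced ON events stop pacing; then 3 × OFF rate for 14 days | 1.52 | 1.61 | 15.9% |
| As above, 50% stop | 1.50 | 1.66 | 24.5% |
| ON ×1.5; 30% stop; OFF rate afterwards | 1.48 | 1.42 | 7.3% |

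The first row isolates unequal length. It does not move the hazard ratio, because OFF events after day 28 have no ON subject in the risk set; they were 33% of all events and carried no information. A crude rate ratio does move. With ON ×1.5 and OFF rates halving after week 8, it was 2.02 under the written rule against 1.52 in the common window.

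**4. Withdrawal phase.** With equal rates to week 8 and a doubled ON rate in weeks 8 to 12, the written rule gave 0.99. A week 4 to 12 comparison gave 1.51 and the SAP code gave 1.42. The code falls short of 1.51 because it writes no closing interval for a subject with exactly one AE.

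**The case against.** The strongest reply is that the subject rule should be read with its heading and methods. Under an 8 week heading and a week 4 to 8 comparison, the OFF phrase may mean the full week 4 to 8 period. The only asymmetry left is then ON subjects who stop early. This reading is plausible, and the documents do not establish that OFF runs to week 12. It does not rescue the rule, because early stopping is where the informative censoring arises.

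A reader might infer that ON events after stopping are lost and that the ON withdrawal phase enters no AE analysis at all. The documents do not support that. The sample code counts those events to exit, and SAP 7.9.8 allows any test to be repeated at week 12. That provision is optional, however, and sits under an efficacy endpoint.

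A reader might also infer that the comparison is tilted towards making ON look safe. It need not be. An event that prompts stopping occurs during pacing and is counted, and an on-pacing rate avoids dilution by unpaced time. The last row of the table shows the reversal.

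Two further limits stand. Protocol 10.15 lists intolerable symptoms that reprogramming cannot alleviate among the reasons for study exit, and events after exit are unavailable under any rule. The protocol's interest in withdrawal (5.1: "includes monitoring the reaction of the heart to withdrawal of the pacing therapy") concerns cardiac response, and Protocol 7.2 names quality of life, walk test, echo and activity for that phase. An AE summary there is sensible, but it is not a stated objective that the plan fails to meet.

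**Conclusion.** The point holds as an inconsistency with a specific defect inside it. The week 4 to 8 AE comparison has three incompatible windows, and the one in the subject rule censors a single randomised arm at an outcome-related time. Under the assumptions tried, early stopping moved the hazard ratio by between −0.16 (1.50 against 1.66) and +0.06 (1.48 against 1.42). Neither sign nor size can be fixed from the documents, because they depend on how often pacing is stopped and on risk afterwards. Unequal length alone is not a source of bias in the hazard ratio; it matters for crude rates and for the length of the cumulative curves. Under the subject rule, ON events after pacing stops, including weeks 8 to 12, enter no mandatory AE analysis, although the code would count them.

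The study is exploratory and unpowered (SAP Section 6), so what is affected is the safety description, not a confirmatory test. It should be corrected before analysis.

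**What to change.** In SAP 7.9.3 and Protocol 14.1.3:

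- Make the main comparison all AEs from randomisation to the 8 week visit, both arms as randomised, regardless of pacing status.
- Keep the on-pacing rate in ON as a supplementary summary.
- Add a week 8 to week 12 AE summary by arm.

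In the SAP code:

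- Add the 8 week visit date, count only events on or after randomisation, and censor both arms at the earlier of that visit and study exit.
- Write a closing interval for every subject, including those with one AE.
- Take the pacing-stop date for the supplementary rate from the crossover records and device interrogations.

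The cost is wording in two documents and minor reprogramming; AEs are already collected to exit. The main comparison may be diluted by unpaced ON time, which the supplementary on-pacing rate covers. Nothing changes in how subjects are managed.

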#### 7.9.4. Ancillary Efficacy Endpoint - Quality of Life

##### **MNLWHF Questionnaire – 4 weeks**

###### Hypothesis

There is an improvement in quality of life of an additional 4 week period of elevated night pacing after an initial 4 week period of elevated night pacing compared to that period of 4 weeks with the elevated night pacing programmed OFF after the initial 4 weeks period of elevated night pacing, as assessed by the MNLWHF questionnaire.

###### Analysis Methods

A paired comparison of the value at the end of the period compared to the value at the start of the period will be calculated. A one-sided paired t-test will be performed testing the hypothesis

$$H_0: \mu \leq 0$$

$$H_a: \mu > 0$$

Where  $\mu$  = difference in quality of life score from baseline to week 4 visit

Quality of life is assessed via the MNLWHF questionnaire by the sum of the response values of the 21 questions. If not all, but at least 17 of the questions on the questionnaire are completed, the score will be summed and normalized to a scale of 0-105, based on the number of questions answered.

SAS code similar to the following will be used to evaluate the 4 week MNLWHF endpoint:

```
PROC TTEST;  
  PAIRED mnlwhf0*mnlwhf4;  
RUN;
```

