There are differential rates of adverse event reporting between subjects randomized to receive elevated night pacing and subjects randomized to elevated night pacing OFF. In addition, adverse events for subjects continuing to receive elevated night pacing will be characterized and extended from the AE's collected during the first 4 weeks.

Analysis Methods

The adverse reporting rate during the period from week 4 to week 8 in subjects in the ON arm and OFF arm will be compared and characterized.

Determination of Subjects for Analysis

Rates of adverse events for subjects randomized to OFF will be calculated over the full period of follow-up, while rates of adverse events for subjects randomized to ON will be calculated only during the period that subjects were actually receiving elevated night pacing.

**14.1.4. Ancillary Efficacy Endpoint - Quality of Life****MNLWHF Questionnaire – 4 weeks**Hypothesis

There is an improvement in quality of life from baseline after a 4 week period of elevated night pacing, as assessed by the MNLWHF Questionnaire.

Analysis Methods

A paired comparison of the value at the end of the period compared to the value at the start of the period will be calculated. A one-sided paired t-test will be performed testing the hypothesis

$$H_0: \mu \leq 0$$

$$H_a: \mu > 0$$

Where  $\mu$  = difference in MNLWHF score from baseline to week 4 visit

Determination of Subjects for Analysis

All subjects that completed 4 weeks of elevated night pacing. Subjects that were unable to tolerate or withdrew from the treatment during the first 4 weeks because of safety or other issues will not be included in this efficacy analysis.

**MNLWHF Questionnaire – 8 weeks**Hypothesis

There is an improvement in quality of life of an additional 4 week period of elevated night pacing after an initial 4 week period of elevated night pacing compared to that period of 4 weeks with the elevated night pacing programmed OFF after the initial 4 weeks period of elevated night pacing, as assessed by the MNLWHF Questionnaire.

Analysis Methods

A paired comparison of the scores at the 8 week visit compared to the scores at the 4 week visit period will be calculated. A one-sided paired t-test will be performed testing the hypothesis

$$H_0: \mu_{ON} \leq \mu_{OFF}$$

$$H_a: \mu_{ON} > \mu_{OFF}$$

Where  $\mu_{ON}$  = difference in MNLWHF score from week 4 to week 8

Determination of Subjects for Analysis

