#### Analysis Methods

A paired comparison of the scores at the 8 week visit compared to the score at the 4 week visit period compared to the value at the start of the period will be calculated. A one-sided paired t-test will be performed testing the hypothesis

$$H_0: \mu_{ON} \leq \mu_{OFF}$$

$$H_a: \mu_{ON} > \mu_{OFF}$$

Where  $\mu_{ON}$  = difference in quality of life score from week 4 to week 8

SAS code similar to the following will be used to evaluate the effect of the study therapy on the MNLWHF endpoint between week 4 and week 8:

```
PROC TTEST;
  CLASS trt;
  VAR mnlwhfdiff;
RUN;
```

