#### Analysis Methods

A paired comparison of the value at the end of the period compared to the value at the start of the period will be calculated. A one-sided paired t-test will be performed testing the hypothesis

$$H_0: \mu \leq 0$$

$$H_a: \mu > 0$$

Where  $\mu$  = difference in EQ-5D-5L score from baseline to week 8 visit

The EQ-5D-5L summary health score is calculated based on five “dimension” questions: mobility, self-care, usual activities, pain/discomfort, anxiety/depression. Each dimension has five options which are: 1=no problem, 2=slight problem, 3=moderate problem, 4=severe problem, 5=unable to perform.

SAS code similar to the following will be used to evaluate the 8 week EQ-5D-5L endpoint:

```
PROC TTEST;
  PAIRED eq5d0*eq5d8;
RUN;
```

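### The one-sided quality-of-life tests count a positive change as improvement, but the plan never says which end of either score is better, and text and SAS code disagree on sign and sidedness

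*SAP*

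**What the plan says.** **MNLWHF, 4 weeks.** The CIP hypothesis (14.1.4) is: "There is an improvement in quality of life from baseline after a 4 week period of elevated night pacing, as assessed by the MNLWHF Questionnaire". SAP 7.9.4 (MNLWHF Questionnaire – 4 weeks, Analysis Methods) says "A one-sided paired t-test will be performed testing the hypothesis" and gives H0: mu ≤ 0 against Ha: mu > 0, with mu the "difference in quality of life score from baseline to week 4 visit". It describes the comparison as the end of the period against its start. The score is the sum of 21 items; when 17 to 20 are answered, "the score will be summed and normalized to a scale of 0-105, based on the number of questions answered". The sample code is `PAIRED mnlwhf0*mnlwhf4`, with no option for a one-sided test.

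**MNLWHF, 8 weeks.** The alternative is mu_ON > mu_OFF, with mu_ON the "difference in quality of life score from week 4 to week 8". The code is a two-group t-test on a difference variable whose sign is not defined in that section.

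**EQ-5D-5L, 8 weeks.** Both one-sided alternatives again point upwards (mu > 0 and mu_ON > mu_OFF). The SAP lists the level codes: "1=no problem, 2=slight problem, 3=moderate problem, 4=severe problem, 5=unable to perform". It says that a summary health score is calculated from the five dimensions and gives neither a formula nor a value set.

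**6 Minute Walk.** SAP 7.9.5 uses the same alternatives and the same order of variables in the paired code (baseline first, week 4 second).

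**The concern.** A one-sided test needs a declared direction of benefit. For walk distance the direction is obvious: further is better. The same template has been applied to two questionnaires, one with no stated direction and one whose item levels rise with the severity of the problem.

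If a higher score is worse and the change is later minus earlier, a real improvement gives a p-value near 1. A real deterioration gives a small p-value attached to a hypothesis headed improvement.

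The result is also used later. SAP 4.2 and 7.9.8 choose measures for the sustained-effect tests according to whether they were significant at week 4 or between arms at week 8, so a wrong direction could send the wrong measures forward. SAP 7.10 lists a known error in the CIP's statistical section, but not this one.

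**Working it through.** The plan states no power or effect size for these endpoints, so there is no figure to reproduce.

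**Step 1: can one subtraction order serve both endpoints?** Assume that a higher MNLWHF score is worse.

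| Definition of mu | Ha: mu > 0 for walk distance | Ha: mu > 0 for MNLWHF |
|---|---|---|
| Later minus earlier (natural reading of the text) | tests for benefit | tests for worsening |
| Baseline minus follow-up (order in the code) | tests for worsening | tests for benefit |

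Neither order makes both hypotheses right. Under the assumption, at least one endpoint is misdirected whichever order was meant.

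**Step 2: EQ-5D-5L.** A sum of five levels coded 1 to 5 runs from 5 (no problems) to 25 (worst), so under later minus earlier Ha: mu > 0 would test for worsening. For an index on which higher is better, Ha: mu > 0 is correct. The SAP does not say which is meant.

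**Step 3: what the code does.** In PROC TTEST, `PAIRED a*b` analyses a minus b, so the MNLWHF and EQ-5D-5L code takes baseline minus follow-up. Without a `SIDES=` option the p-value is two-sided. In the two-group code, with trt coded 0 for control and 1 for treatment as in SAP 7.9.3, the reported difference is OFF minus ON, opposite to mu_ON − mu_OFF.

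**Step 4: size.** Inputs from the documents: up to 30 subjects (CIP 14, SAP 6) and 2:1 allocation (SAP 5.1), hence at most 30 pairs, or 20 ON versus 10 OFF. Assumptions, because the documents give none: one-sided alpha 0.05 (two-sided 0.05 for the code) and a true benefit of 0.2 to 1.0 SD of the change.

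*Paired test.* The statistic is noncentral t with df = n − 1 and noncentrality d√n. For n = 30 and d = 0.5 this is 0.5 × √30 = 2.739, with critical values 1.699 (one-sided) and 2.045 (two-sided).
- Ha towards benefit: P(T > 1.699) = 0.848.
- Ha against benefit: P(T < −1.699) = 0.0000077.
- Two-sided code: P(|T| > 2.045) = 0.754.

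| True benefit (SD), 30 pairs | Ha towards benefit | Ha against benefit | Two-sided code |
|---|---|---|---|
| 0.2 | 28% | 0.33% | 19% |
| 0.3 | 48% | 0.06% | 36% |
| 0.5 | 85% | 0.0008% | 75% |
| 0.8 | 99.6% | <0.0001% | 99% |

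With 25 pairs and 0.5 SD: 78%, 0.002% and 67%. By symmetry, with 30 pairs a true worsening of 0.5 SD would be declared improvement 85% of the time by a test pointing against benefit.

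*ON versus OFF.* df = 28 and noncentrality d / √(1/20 + 1/10). At d = 0.5 this is 0.5 / 0.3873 = 1.291, with critical values 1.701 and 2.048.

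| True benefit (SD), 20 v 10 | Ha towards benefit | Ha against benefit | Two-sided code |
|---|---|---|---|
| 0.3 | 19% | 0.8% | 12% |
| 0.5 | 35% | 0.18% | 24% |
| 0.8 | 64% | 0.01% | 51% |
| 1.0 | 81% | 0.002% | 70% |

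**The case against.** A reader might infer that both questionnaires demonstrably score problems upwards and that the trial would therefore miss a true quality-of-life benefit. The documents do not support that, for four reasons.

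- **MNLWHF direction.** Only the EQ-5D-5L level codes show a direction. The MNLWHF is described as a sum on 0-105 and no more, so that part stays conditional.
- **Subtraction order.** The text never writes it. The only explicit order, in the sample code, is baseline minus week 4. With mu so defined, Ha: mu > 0 would point to benefit on a higher-is-worse score. This does not settle intent: the text compares end with start, and the walk-test code uses the same order, where it would be wrong.
- **Sidedness.** The code as printed is two-sided and would show a change of either sign. The near-zero probabilities apply only to the one-sided text, read as later minus earlier. Against this, the SAP offers the code only as similar to what will be run, while the text specifies one-sided tests.
- **EQ-5D-5L.** Nothing says that the levels are summed. What is shown is a missing scoring rule, not a reversed test.

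On consequence, the objection also carries weight. The study is not powered for any endpoint, it makes no multiplicity adjustment, and it names the 4-week safety and tolerability result as the one that helps decide whether to proceed. SAP 7.9.8 also allows any test at week 12 regardless of earlier significance. These facts lower the severity but do not supply the missing direction.

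**Conclusion.** The point holds in conditional form. Direction of benefit, sign of mu, sidedness and EQ-5D-5L scoring are each undefined or inconsistent between text and code. If a higher MNLWHF score is worse and mu is later minus earlier, the written MNLWHF alternatives test for worsening at both time points; the EQ-5D-5L alternatives do so under the same order if levels are summed.

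For a 0.5 SD benefit, the text so read cuts the chance of declaring improvement from 85% to under 0.001% at 4 weeks, and from 35% to about 0.2% for ON versus OFF. The two-sided code keeps 75% and 24%. These figures rest on the assumed alpha and effect sizes and on the maximum of 30 subjects; the analyses exclude those who did not complete the first 4 weeks, so actual numbers may be lower.

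Because the endpoints are ancillary and unpowered, this should be corrected but does not threaten the trial's main purpose. It should be done before data freeze and unblinding, the point by which CIP 14 requires the SAP to be complete: choosing the direction of a one-sided test after seeing results would defeat pre-specification.

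**What to change.** In SAP 7.9.4 and CIP 14.1.4, with matching code in SAP 7.9.5:

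1. State for each score which direction is better.
2. Define mu as later minus earlier throughout.
3. Set the alternatives to match. For MNLWHF, if higher is worse, use Ha: mu < 0 at 4 weeks and Ha: mu_ON < mu_OFF from week 4 to week 8.
4. Name the EQ-5D-5L scoring method. Keep the upward alternatives for an index on which higher is better; reverse them for a level sum.
5. Align the code with the text: the order in `PAIRED`, the definition of each difference variable, the order of the trt groups, and an explicit `SIDES=` option. Include the 6 Minute Walk: adding `SIDES=U` to its present code would test for a fall in distance.
6. Replace the hypothesis under MNLWHF Questionnaire – 4 weeks in SAP 7.9.4, which repeats the 8-week ON-versus-OFF text, with the CIP's change-from-baseline hypothesis.

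The cost is wording and a few lines of code. No new data are needed.
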